In the traditional counting condition books, children were instructed to count the objects on each side of the page and choose which side had more objects. All objects in the traditional counting condition were the same size. This was repeated for 20 question pages, with feedback pages following each question page. In the non-numerical condition books, a single item appeared on the question page and children were instructed to name the object or animal that appeared on the pages and then describe either the color of the object/animal or the sound that the object/animal makes. Again, there were 20 question pages with feedback pages following each of them. The traditional counting condition control allowed us to rule out the possibility that it is simply the exposure to counting that drives the effect on math performance, and the non-numerical condition controlled for any influence that generally interacting with researchers may have had on performance.

Each child was randomly assigned to a condition within classroom so that each condition was approximately equally represented in each classroom, and the four one-on-one sessions consisted of experimenters reading to participants from different books of the same condition. Regardless of conditions, children had a choice between two tales that shared the same basic premise: Laura and Lamar visit a park, or Amaya and Oscar visit a zoo. In the first tale, the characters looked for a lost dog, while a penguin was used in the second. In each case, the story started with the animal going missing, and the characters had to complete tasks to find it. All conditions used the same objects and backgrounds and included the same number of pages. The

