word count on each page was similar across conditions. In the traditional counting, size-to-number, and mixed conditions, the number of objects on each side of the page followed three different simplified ratios: 1:3, 2:3, 1:2. Each page followed these ratios using between 2 and 10 objects on each side of the page, to make sure that the numbers were within the range of numbers which preschool age children are familiar with. The size-to-number and mixed book conditions also varied the total area of objects on each side of each page based on these same three simplified ratios. The ratio of the total area on each side was the inverse of the ratio of total objects on each side. For instance, in a trial where the left side of the page contained 2 objects and the right side contained 4 objects (1:2 ratio), the objects on the left side had a total area that was twice the total area of the objects on the right side (See Figure 2 to view sample pages for each condition). The correct answer was distributed evenly across the right and left sides of pages.

Power Analysis and Exclusion Criteria. A power analysis conducted in G*Power for a 2 (timepoint: pre-intervention and post-intervention) x 4 (condition: counting, mixed, non-numerical, size-to-number) ANOVA, and a within-between interaction, revealed a necessary sample size of 84 participants for the study (21 participants per group). We assumed a medium effect size ($\eta_p^2 = .02$), 2 timepoints, 4 between-participants groups, and a correlation between pre-intervention and post-intervention of $r = .4$ for the power analysis. We initially recruited 169 participants for the study, knowing that school absences during a short-term weeklong study would likely significantly reduce the final sample size. There were 116 participants in the final sample size (Size-to-Number condition $n = 37$, Mixed condition $n = 25$, Counting condition $n = 30$, Non-numerical condition = 24) who were present at all pre-intervention and post-intervention assessments and book reading sessions and had complete assessment data. We randomly

assigned children within each condition to either the number first FAM assessment or the size first FAM assessment (number first n = 61, size first n = 55). Participant exclusions were primarily due to school absences (n = 28), children not wanting to participate in one or more assessments (n = 13), developmental delays (n = 1), and technical errors with the online data collection system (n = 11).

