Analytic Plan

Primary Analyses. Our primary research question was if children in the experimental FAM conditions significantly improved their FAM skills from pre-intervention to post-intervention. We did not have a prediction about whether one of the experimental FAM conditions would outperform the other experimental FAM condition. We conducted a repeated-measures ANOVA with timepoint (pre-intervention and post-intervention) as the within-participants factor and condition (size-to-number, mixed, counting, non-numerical) as the between-participants factor, controlling for age, gender, and EF skills. We analyzed planned contrasts for the condition by timepoint interaction that included a complex contrast testing for differences between the experimental (mixed and size-to-number) and control groups (counting and non-numerical) in their FAM task changes across timepoints, as well as simple contrasts comparing FAM changes across timepoints within each of the four conditions. We first examined the FAM mixed trials as our outcome of interest given that children were randomly assigned to complete different versions of the FAM task that varied in if the number or size trials were the pre-switch and post-switch trial levels. This mixed level was the trial level that was the same across all conditions. However, we also ran these analyses using the combined FAM post+mixed accuracy variable as this has been the variable used in prior correlational analyses, and we included FAM version as a covariate.

Exploratory Analyses. To explore potential differences in findings across number and size trials in the FAM task, we repeated our primary analyses, but with the number and size trials and pre- and post-intervention scores as the within-participants factor, controlling for FAM version and other covariates used in prior analyses. We also ran the same repeated-measures ANOVA with three other outcomes (global math achievement, number line estimation, and EF skills) to assess for potential transfer effects.

Results

Descriptive Statistics and Correlations

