given that children completed either the number or size trials at post-switch. Overall, we did not find a significant interaction effect for timepoint x condition (Wilks' Lambda $F(3, 105) = .98, p = .591, \eta_p^2 = .02$). We then examined our planned contrasts. First, we examined pre-intervention to post-intervention change in FAM task performance within each condition, and then compared the two experimental conditions to the two control conditions. All of these contrasts yielded null findings, suggesting that the intervention changes we observed were due primarily to differences within the FAM mixed trial level rather than the FAM post-switch trial level.

Potential Transfer Effects. We examined pre-intervention to post-intervention changes in overall math achievement, number line estimation, and EF skills. We continued to covary age and gender, and for the math achievement and NLE analyses, we covaried pretest EF skills as a general skill variable. For overall math achievement, we did not find a significant interaction between timepoint and condition (Wilks' Lambda $F(3, 109) = .61, p = .605, \eta_p^2 = .02$), nor did we find significant differences within either experimental or control groups in their pre- to post-intervention FAM score changes. For NLE scores as the outcome variable, we did not find an overall interaction effect between timepoint and condition (Wilks' Lambda $F(3, 109) = 1.82, p = .618, \eta_p^2 = .02$). For planned contrasts, we did not find any significant differences across specific conditions in change from pre-intervention to post-intervention. Combining the two experimental conditions and the two control conditions for the complex contrast, we found a significant difference between the changes in NLE scores of experimental and control groups (Wilks' Lambda $F(1, 111) = 5.17, p = .025, \eta_p^2 = .04$) such that the experimental conditions overall significantly improved their NLE scores from pre- to post-intervention (NLE Pre-Int total = 1.60, SE = .26; NLE T2 total = 2.07, SE = .29; Wilks' Lambda $F(1, 111) = 4.40, p = .038, \eta_p^2 = .04$), while the control conditions did not (NLE Pre-Int total = 2.33, SE = .28; NLE Post-Int total

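### The counting arm is meant to exclude a counting-exposure explanation, but the only planned between-group contrast pools it with the non-numerical arm and so does not test this

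*Combined protocol and SAP*

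**What the plan says.** The Books subsection gives the two control arms different jobs. The counting arm is there to "rule out the possibility that it is simply the exposure to counting that drives the effect on math performance". For the other control, "the non-numerical condition controlled for any influence that generally interacting with researchers may have had on performance".

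The Analytic Plan (Primary Analyses) specifies a four-level condition by timepoint interaction and two kinds of planned contrast. One is "a complex contrast testing for differences between the experimental (mixed and size-to-number) and control groups (counting and non-numerical"), which averages the two controls. The other is "simple contrasts comparing FAM changes across timepoints within each of the four conditions", which is pre-to-post change inside one arm at a time. No contrast of the experimental arms with counting is listed.

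The Results (Potential Transfer Effects) report the one significant between-group difference on a numerical outcome. It is for NLE, F(1, 111) = 5.17, p = .025, and was obtained by "Combining the two experimental conditions and the two control conditions for the complex contrast".

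**The concern.** The rival explanation comes from the documents themselves: children who practise counting may improve whether or not they practise switching between size and number. To exclude it, the experimental arms must be compared with the counting arm. Averaging counting with an arm that has no numerical content mixes two questions. If counting exposure helped the experimental and counting arms and not the non-numerical arm, the pooled contrast could be positive with no effect specific to the FAM books.

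The other planned tests do not fill the gap. The omnibus interaction keeps counting separate, but it has no direction and is not specific to counting (FAM mixed trials: p = .41). The within-arm result for counting (p = .463) is not a comparison, because significance in one arm and not in another does not test the difference between them.

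At stake is what may be said about mechanism, above all for NLE.

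**Working it through.** **Inputs.** Analysed n (Power Analysis and Exclusion Criteria): size-to-number 37, mixed 25, counting 30, non-numerical 24. Within-arm F for change in FAM mixed trials (Results, Primary Analyses): mixed 8.65, size-to-number 4.77, counting .54, non-numerical 1.77. NLE means and F values are from Potential Transfer Effects. Everything rebuilt here assumes a common SD of change and ignores covariate adjustment of the standard errors, so it is approximate.

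**1. Reproduce the printed figures.** Change per arm in SD-of-change units is d = √(F/n):
- mixed √(8.65/25) = .588
- size-to-number √(4.77/37) = .359
- counting √(.54/30) = .134
- non-numerical √(1.77/24) = .272

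The n-weighted mean is .332. Omnibus F = Σn(d − .332)²/3 = (1.639 + .027 + 1.176 + .088)/3 = .98, p = .41; the printed values are .96 and .41. All changes are taken as positive, since a negative sign in either or both control arms gives F of 2.57 or more.

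For NLE, the pooled contrast rebuilds as [(√(4.40/62) + √(1.37/54))/√(1/62 + 1/54)]² = 5.23, against the printed 5.17.

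**2. Missing contrasts, FAM mixed trials.** The experimental mean is (.588 + .359)/2 = .474.
- Minus counting: .339, SE √[.25(1/37 + 1/25) + 1/30] = .224, t = 1.52, p = .13, 95% CI −.10 to .78.
- Minus non-numerical: .202, SE √[.25(1/37 + 1/25) + 1/24] = .242, t = .84, p = .40, 95% CI −.28 to .68.

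**3. Pooled contrast if counting alone acts.** Suppose all three numerical arms gain delta and the non-numerical arm gains nothing. With equal arm weights the expectation is delta − delta/2 = .50 delta (SE .188). With the arms collapsed to two groups it is delta − (30/54)delta = (24/54)delta = .44 delta (SE .186). Noncentral t, two-sided alpha .05 (assumed), analysed n:

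| delta (SD of change, assumed) | Collapsed | Equal weights |
|---|---|---|
| .3 | 11% | 12% |
| .5 | 22% | 26% |
| .8 | 47% | 56% |

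Now suppose the experimental arms gain only half of delta. This is plausible: 10 of the 20 question pages in the size-to-number books concern number, the mixed books alternate the two dimensions, and the counting books ask for counting on all 20. The expectation is then .5 delta − .5 delta = 0 (equal weights), or .5 delta − (30/54)delta = −.06 delta (collapsed).

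**4. NLE bound.** The experimental arms changed by 2.07 − 1.60 = +.47 and the pooled controls by 2.07 − 2.33 = −.26. If counting explained the whole gain, the counting arm also gained .47. The non-numerical arm must then have changed by (54 × −.26 − 30 × .47)/24 = −1.17 points, or by 2 × −.26 − .47 = −.99 with equal weights.

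The SD of change implied by the printed F values is .47/√(4.40/62) = 1.76 or .26/√(1.37/54) = 1.63. With n = 24, t runs from −.99/(1.76/√24) = −2.75 to −1.17/(1.63/√24) = −3.52, all p < .01. The Results report no significant condition-specific finding for NLE change.

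**The case against.** The strongest reply is that the rival explanation fits the printed data poorly. It requires counting to match the experimental arms and exceed the non-numerical arm. On FAM mixed trials counting changed least (.134, against .272 for non-numerical), and the rebuilt contrast is larger against counting than against non-numerical. Here pooling diluted the counting comparison. For NLE, step 4 shows that a full counting-only account needs a drop in the non-numerical arm that sits badly with the reported absence of condition-specific findings. Both points stand. They make the rival less likely, but they do not replace the missing test, and a partial contribution to the NLE result remains open.

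It may also be said that the Results already cover arm-level NLE comparisons, since they mention specific conditions. The wording is ambiguous. If it means between-arm comparisons, experimental versus counting was not significant. If it means within-arm change, the comparison was not made. Neither reading supports ruling counting out.

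Three stronger readings are tempting and are not supported:
- **The pooled contrast credits the FAM books wrongly about half the time.** That needs a counting gain near .8 SD, which the documents do not give and which exceeds every rebuilt FAM change (largest .588). It also needs equal gains in all three numerical arms.
- **The NLE finding is a counting artefact.** Step 4 argues against this.
- **The study reports that counting was ruled out.** The sentence is design rationale in Measures; the Results draw no such conclusion, and NLE is listed as exploratory.

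**Conclusion.** The concern holds as a gap between a stated purpose and the planned analysis. The counting arm was included to exclude one explanation, and no planned contrast tests it. That follows from the text and needs no assumption.

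The size of any distortion is uncertain. It ranges from about none (experimental arms gain half as much from counting) to .44–.50 delta (equal gains), and delta itself is unknown. For FAM mixed trials the experimental arms are not shown to differ from counting (p about .13, interval including zero), although the pattern does not favour the counting explanation. For NLE only a partial counting contribution stays open. The planned pooled analysis remains valid for the broader question it asks, experimental against control books on average.

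**What to change.** In the four-arm model, add two 1-df contrasts in change: the mean of mixed and size-to-number minus counting, and the same mean minus non-numerical. Report both for FAM mixed trials, NLE and math achievement, with estimates and 95% confidence intervals, labelled as additional to the planned contrasts. Keep the pooled contrast as planned. Reword the Books subsection so that counting exposure is said to be ruled out only if the experimental-versus-counting contrast supports it.

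The cost is two contrast lines in a model already fitted, with no new data. The downside is lower precision, because the counting arm has 30 children: the rebuilt SE is .224, against .188 for the pooled contrast. The claim may have to be softened.

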compared to control groups (counting, non-numerical). Overall, we did not find a significant interaction effect for timepoint x condition (Wilks' Lambda $F(3, 109) = .96, p = .41, \eta_p^2 = .03$). We then tested our planned comparisons, as they were driven by our hypothesis that FAM ability can be improved through intervention. Prior studies examining the relevance of planned comparisons supported this decision by encouraging researchers to perform planned comparisons regardless of the outcome of the ANOVA analysis, especially when those comparisons are supported by previous findings or theory ([Ruxton & Beauchamp, 2008](#))

First, we examined pre-intervention to post-intervention change in FAM task performance within each condition, and then compared the two experimental conditions to the two control conditions. Children significantly improved their FAM task performance from pre-intervention to post-intervention within the two experimental groups, mixed (Wilks' Lambda $F(1, 109) = 8.65, p = .004, \eta_p^2 = .07$) and size-to-number (Wilks' Lambda $F(1, 109) = 4.77, p = .031, \eta_p^2 = .04$) (See Figure 3). Children did not significantly improve their FAM task performance in the two control group conditions, counting (Wilks' Lambda $F(1, 109) = .54, p = .463, \eta_p^2 = .01$) and non-numerical (Wilks' Lambda $F(1, 109) = 1.77, p = .186, \eta_p^2 = .02$) (See Figure 3). These findings also held when comparing the two experimental conditions to the two control conditions such that children in the two experimental conditions significantly improved their performance (Wilks' Lambda $F(1, 111) = 12.90, p < .001, \eta_p^2 = .10$) (See Figure 4) while children in the control conditions did not (See Figure 2) (Wilks' Lambda $F(1, 111) = 2.11, p = .150, \eta_p^2 = .02$) (See Figure 4).

FAM Post + Mixed Trial Level Outcomes. We also conducted the same analyses with the exception of the outcome variable being the FAM Post+Mixed task performance as this variable has been used in prior FAM studies (Fuhs et al., 2021). We included FAM version as a covariate

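### Classroom was the randomisation block but appears in no described model; if change varies by classroom the within-condition tests are too liberal, and on the primary outcome the size-to-number gain (p = .031) is the exposed result

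*Combined protocol and SAP*

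**What the plan says.** **Design.** Under Books: "Each child was randomly assigned to a condition within classroom so that each condition was approximately equally represented in each classroom". Classroom is therefore the block for assignment.

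**Model.** Analytic Plan, Primary Analyses, specifies a timepoint-by-condition repeated-measures ANOVA, "controlling for age, gender, and EF skills". The post+mixed version adds FAM version. The transfer models use age and gender, plus pretest EF for math achievement and NLE. Classroom is listed in none of them.

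**Contrasts.** The plan names an experimental-versus-control contrast in change "as well as simple contrasts comparing FAM changes across timepoints within each of the four conditions".

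**Results that use within-group tests.** For FAM mixed trials the interaction was null, F(3, 109) = .96, p = .41. The text then reports: "Children significantly improved their FAM task performance from pre-intervention to post-intervention within the two experimental groups". The values are mixed F(1, 109) = 8.65, p = .004; size-to-number F(1, 109) = 4.77, p = .031; and pooled experimental F(1, 111) = 12.90, p < .001. For NLE, "we found a significant difference between the changes in NLE scores of experimental and control groups" (F(1, 111) = 5.17, p = .025). The text adds that "the experimental conditions overall significantly improved their NLE scores from pre- to post-intervention" (F(1, 111) = 4.40, p = .038).

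**Sample.** Under Power Analysis and Exclusion Criteria: "We initially recruited 169 participants for the study". Of these, 116 were analysed. No count of classrooms, and no count of arms by classroom, is given.

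**The concern.** Randomising within a block and then leaving the block out of the model affects the two kinds of test differently.

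- **Within-condition change.** If some classrooms gain more than others, whatever the condition, children of one condition in the same classroom have correlated changes. The test counts them as independent, so its standard error is too small.
- **Between-condition contrasts.** A shared classroom shift cancels when the conditions are balanced within classrooms, but its variance stays in the error term. The test is then mildly conservative. This direction fails if balance was lost or if the condition effect differs between classrooms.

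The positive FAM statements in the Results rest on within-condition tests, the kind that can become too liberal. At stake is whether a result as close to .05 as the size-to-number gain would survive a model that respects the blocking.

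**Working it through.** **1. Is classroom really absent?** Rebuild the error df as N − groups − covariates, with N = 116.
- FAM mixed, math, NLE: 116 − 4 − 3 = 109, as reported.
- Two-group versions: 116 − 2 − 3 = 111, as reported.
- EF: 116 − 4 − 2 = 110, as reported.
- Post+mixed: 116 − 4 − 4 = 108, but 105 is reported. This one does not reconcile and cannot serve as a check either way.

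A fixed classroom block would have taken K − 1 further df, so the first three sets agree with the text: no classroom term.

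**2. Reproduce the reported figure.** The upper tail of F(1, 109) at 4.77 is .0311, matching p = .031. The 5% critical value is 3.93, so the result tolerates a variance inflation of 4.77 / 3.93 = 1.21.

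**3. Apply clustering of change.** Design effect = 1 + (n/K − 1) × ICC, where n is the number of children in the tested group, spread evenly over K classrooms. F is divided by this and referred to the reported df. The n values come from Power Analysis and Exclusion Criteria (size-to-number 37, mixed 25, pooled 37 + 25 = 62). K and the ICC are assumptions.

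Example, size-to-number, K = 8, ICC .10: 1 + (4.625 − 1) × .10 = 1.3625; 4.77 / 1.3625 = 3.50; p = .064.

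Size-to-number p:

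| ICC | K = 8 | 12 | 16 | 20 | 24 |
|---|---|---|---|---|---|
| .05 | .047 | .040 | .037 | .035 | .033 |
| .10 | .064 | .049 | .042 | .038 | .036 |
| .20 | .099 | .069 | .055 | .046 | .040 |

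The ICC at which p reaches .05 is (1.214 − 1) / (37/K − 1): .059, .103, .163, .252 and .396 for K = 8, 12, 16, 20 and 24.

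**4. The other within-group gains, same formula.**
- NLE, pooled experimental (n = 62, F = 4.40, 111 df): tolerates 4.40 / 3.93 = 1.12. At ICC .10, p = .108 (K = 8) down to .054 (K = 24).
- Mixed FAM (n = 25, F = 8.65): tolerates 8.65 / 3.93 = 2.20. The worst case in the range (K = 8, ICC .20) gives p = .015.
- Pooled experimental FAM (n = 62, F = 12.90): tolerates 12.90 / 3.93 = 3.28. The worst case gives p = .021.

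**5. Between-condition tests, under balance.** If classroom explains a share c of the change variance, F becomes about F / (1 − c).
- FAM interaction at c = .20: .96 / .80 = 1.20, p = .31. To reach the 5% value of 2.69, c would have to be 1 − .96 / 2.69 = .64.
- NLE contrast at c = .05, .10 and .20: F = 5.44, 5.74 and 6.46; p = .021, .018 and .012.

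**6. Simulation** of a model without classroom (arms 37/25/30/24, three covariates, nominal 5%). At ICC .10 the size-to-number test rejects a true null at .096 (K = 8), .074 (K = 12) and .060 (K = 20). The experimental-versus-control test runs at .039–.042 for the same K when conditions are balanced. In a separate run at K = 8 and 16 it ran at .046–.048 with children placed at random over classrooms. With 5% classroom plus 5% classroom-by-condition variance it ran at .058–.089.

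**The case against.** **The ICC is probably small.** This stands. Under Procedure, readings were one-on-one, without added scaffolding, over about four days, so there is little classroom teaching for change to cluster on. Measurement noise also limits the ICC. The baseline FAM mixed score (mean .64, SE .03, n = 61) implies a variance of 61 × .03² = .055. Twelve trials with binomial error account for about .016 of that. With the planning correlation of .4, the noise share of change variance is about .016 / (.6 × .055) = .48 (.32 to .76 for SE .035 to .025). An ICC of .20 would then need classroom to carry about .20 / .52, or 40%, of true change variance (29–85%). This is rough, since the SE is rounded and r is a planning assumption, but it makes the bottom row of the table unlikely.

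**K may be large.** This also stands. K = 8 means 169 / 8 = 21 recruited children per classroom; K = 24 means 7. Nothing in the documents excludes 20 to 24, where size-to-number stays below .05 up to ICC .20.

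**A reader might refer the adjusted F to K − 1 df** and conclude that size-to-number fails even without clustering (at ICC 0, p = .065 at K = 8 and .052 at K = 12). The documents do not support that. K − 1 df is the price of estimating the between-classroom variance. Charging it on top of a known design effect counts the penalty twice: in simulation such a test has size of about .02 at K = 8 and .03 at K = 12. At ICC 0 the reported p = .031 is correct.

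**Nothing substantive changes.** Largely true for FAM. The pooled experimental gain stands without size-to-number.

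**Conclusion.** The concern holds, in limited form. Classroom is the randomisation block and is in no described model. The within-condition tests are too liberal if, and only if, change varies by classroom. On the primary outcome this exposes one result: size-to-number stays below .05 at ICC .05 for every K considered, passes .05 at ICC .10 only for K = 8, and at ICC .20 for K = 8 to 16. The exploratory within-group NLE gain is more fragile. These ranges rest on assumed K and ICC and on an even spread of children over classrooms.

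Two stronger readings are not supported. The first is that the omission undermines the FAM results as a whole: the mixed and pooled gains stay below .05 across the range, and the interaction very likely stays null. The second is that it weakens the randomised NLE contrast (p = .025): under balance, that p would fall. With 169 − 116 = 53 children excluded and no counts by classroom, balance cannot be confirmed, so the direction for between-condition tests stays open.

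The planned experimental-versus-control contrast for FAM mixed is not reported. That is a separate issue, which modelling classroom would not cure, and it adds no weight here.

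**What to change.** Re-fit with classroom acting on change.

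- **Between-condition contrasts:** model the change score, or post-test adjusted for pretest, on condition, that outcome's planned covariates, and classroom as a fixed block or random intercept. As a sensitivity check for an effect that differs by classroom, add classroom-clustered standard errors with a small-sample correction.
- **Any within-condition test:** use a random classroom effect on change, or clustered standard errors with a small-sample correction.
- **Report** the number of classrooms, arm counts per classroom and the ICC of change. These settle which cell of the table applies. Until then, describe the size-to-number gain as sensitive to classroom clustering.

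**Cost.** No new data, since the assignment procedure already used classroom. A fixed block takes K − 1 error df: 109 falls to 102 (K = 8), 94 (K = 16) or 86 (K = 24). That barely matters between conditions; at unchanged F, the NLE contrast stays at p = .025 with 104, 96 or 88 df. Within conditions, clustered standard errors on about K − 1 df lose real power. That loss is a cost of the remedy, not evidence that the reported p is wrong.

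### The stated requirement of 84 participants does not follow from the power analysis's own inputs: at an assumed alpha of .05 they give about 48% power at 84, and 80% power needs 168

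*Combined protocol and SAP*

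**What the plan says.** The only sample-size justification is in the combined protocol and SAP, under Power Analysis and Exclusion Criteria. It names the software (G*Power), the design (2 timepoints by 4 conditions) and the effect tested (the within-between interaction), and says that the calculation "revealed a necessary sample size of 84 participants for the study (21 participants per group").

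The inputs follow: "We assumed a medium effect size ($\eta_p^2 = .02$), 2 timepoints, 4 between-participants groups". The pre-post correlation completes the list: "and a correlation between pre-intervention and post-intervention of $r = .4$ for the power analysis". Neither alpha nor target power is given for this calculation.

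The same paragraph reports 169 recruited and then: "There were 116 participants in the final sample size", split 37, 25, 30 and 24 across the conditions.

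Two other places give context. The Analytic Plan (Primary Analyses) adds to the interaction test a "complex contrast testing for differences between the experimental (mixed and size-to-number) and control groups (counting and non-numerical"). The Results (FAM Mixed Trial Level Outcomes) report the interaction itself: "we did not find a significant interaction effect for timepoint x condition (Wilks' Lambda $F(3, 109) = .96, p = .41".

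**The concern.** The paragraph gives enough to repeat the calculation except for alpha and target power, and the conventional values of those two do not lead to 84. At the usual 5% level the stated inputs give roughly even odds of detecting the effect with 84 children, which is not what a reader takes a necessary sample size to mean.

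What is at stake is how accurately the planned sensitivity is reported. A reader who wants to know what the interaction test could detect is told that 84 were enough for an effect of .02 and that 116 were analysed, and will conclude that there was power to spare. If .02 and .4 were the real inputs, that conclusion is wrong. If one of them was misreported, the reader does not know what effect the study was sized for.

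The consequence stops there. The document does not use the non-significant interaction to argue that there is no effect, and its positive claims rest on the planned contrasts, not on the figure of 84.

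**Working it through.** **Inputs from the Power Analysis paragraph.** Groups k = 4; timepoints m = 2; partial eta-squared = .02; pre-post correlation r = .4; stated N = 84, equal groups of 21.

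**Assumed, because not stated.** Alpha = .05 and target power = 80%, with ranges shown below. Sphericity is not an issue with two timepoints. Covariates are ignored, since no variance-explained figure is given.

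**Formulae (G*Power default for a within-between interaction).**
- f² = partial eta-squared / (1 − partial eta-squared) = .02/.98 = .0204, so f = .143
- noncentrality λ = f² × N × m / (1 − r)
- df1 = (k − 1)(m − 1) = 3; df2 = (N − k)(m − 1) = N − 4
- power = probability that a noncentral F(df1, df2, λ) exceeds the central F critical value

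**Attempt to reproduce 84.** λ = .0204 × 84 × 2 / .6 = 5.714, with df 3 and 80 and a 5% critical value of 2.72. Power = 47.6%. A simulation of the same design (20,000 runs, 21 per group) gave 47.8%.

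**N required at alpha .05, in equal groups.** N = 164 gives 79.9%; N = 168 (λ = 11.43) gives 81.0%. So 80% power needs 168, or 42 per group, which is 168/84 = 2 times the stated figure. For 90% power, 216 are needed.

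**Do the unstated settings rescue 84?** Required N by alpha and target power, with power at 84:

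| Alpha | 80% | 85% | 90% | 95% | Power at N = 84 |
|---|---|---|---|---|---|
| .01 | 236 | 260 | 292 | 340 | 24.3% |
| .05 | 168 | 188 | 216 | 260 | 47.6% |
| .10 | 136 | 152 | 180 | 220 | 60.6% |
| .20 | 100 | 116 | 140 | 176 | 74.6% |

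No cell is 84 or less. On the stated inputs, 84 is the smallest equal-group N only if alpha is about .263 to .282 at 80% power, or if the target is above 45.4% (the power at N = 80) and at most 47.6% at alpha .05.

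**Does another effect-size option rescue it?** Under the SPSS-type option, λ = f² × (N − k)(m − 1) = .0204 × 80 = 1.63 at N = 84. Power is 15.7%, and 80% power needs 544. This moves further from 84.

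**Which single change to an input would return 84 (alpha .05, 80% power)?**
- Partial eta-squared between .0393 and .0412, with r = .4. At .04, power is 80.8% with 84 and 78.6% with 80, so 84 is exactly the answer.
- r between .701 and .715, with partial eta-squared = .02.

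**Power at the analysed N = 116, if .02 was the real input.** λ = .0204 × 116 × 2 / .6 = 7.891, df 3 and 112, power 63.1%. With r = .3 it is 55.7%; with r = .5 it is 71.9%. These figures treat the groups as balanced and omit covariates. They apply to the 3-df interaction, not to the 1-df experimental-versus-control contrast.

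**The case against.** The strongest reply accepts the arithmetic and disputes the diagnosis. A misreported effect size or correlation is not the only ordinary explanation. If the design was entered the wrong way round, as 2 groups with 4 measurements, then with .02, r = .4, alpha .05 and 80% power the interaction has df 3 and 3(N − 2), and the required N is 82 (80.3% power; 79.2% at 80). Rounded up to four equal groups, that becomes 84. The effect size and correlation would then be correctly reported. This is possible but cannot be shown from the document. The calculation itself returns 82, and 84 would still be wrong for the design described. What stands is practical: the check should also cover the test selected and the numbers of groups and measurements.

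A second reply is that the study is complete, 116 exceeds 84, and no result depends on the calculation. The last part is right and limits the consequence to reporting. But exceeding 84 reassures only if 84 is right for the stated effect, and 116 is below 168.

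A third is that the 63% figure ignores the unequal groups (37, 25, 30, 24) and the adjustment for age, gender and EF. That is so. It should be given only with those caveats, and only if .02 proves to be the real input.

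**Conclusion.** The concern holds. From partial eta-squared .02, r = .4, four groups and two timepoints, 84 cannot be obtained at any conventional alpha and power. At an assumed alpha of .05, power at 84 is 47.6% and an assumed 80% target needs 168.

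This does not establish that the study was planned too small. Barring unconventional settings, the error lies either in the sample size or in what is reported as having been entered, and the document does not settle which. The wording is wrong in either case. Confidence in the non-reproduction is high; the point should be fixed, but it changes no reported result.

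**What to change.** Retrieve the saved G*Power output and report what was entered: the test, the numbers of groups and measurements, the effect size and effect-size option, the correlation, alpha and target power. Correct whichever figure is wrong, and make sure the description of the effect as medium fits the value finally reported. An effect size should not be chosen because it reproduces 84.

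Only if .02 and .4 were the real inputs:
- restate the requirement as 168 for 80% power at alpha .05;
- state that the 116 analysed give about 63% power for the 3-df interaction at that effect (balanced groups, planning correlation, no covariates);
- add that this figure does not describe the 1-df contrast.

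The cost is one look-up and one reworded paragraph. No enrolment or reanalysis is needed. The one drawback, if .02 was the real input, is a less favourable statement of sensitivity.
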